6.13. Efficacy Analyses

For submission of Study GPHK to the US FDA to support the registration of tirzepatide for chronic weight management, all primary and key secondary efficacy assessments will be guided by the “hybrid” estimand conducted using the FAS. Assessment of the primary and key secondary objectives (except for endpoint “delaying the onset of diabetes during 176 weeks or 193 weeks [for participants with prediabetes at randomization]”) will be conducted with multiple imputation of missing data (see Section 6.13.1.3).

For other regulatory agencies, publications and other purposes, the assessment of efficacy objectives will be guided by the “efficacy” estimand using the EAS.

6.13.1. Primary Efficacy Analysis

The primary efficacy measure will be percent change in body weight from randomization **and** percentage of participants who achieve $\geq 5\%$ body weight reduction at 72 weeks. The percent change in body weight at each nominal visit is defined as:

*(postbaseline body weight [kg] – baseline body weight [kg]) / baseline body weight [kg] * 100%.*

Both percent change in body weight and percentage of participants who achieve $\geq 5\%$ body weight reduction will be summarized by treatment and nominal visit (week) from randomization to 72 weeks.

6.13.1.1. Analysis Related to the Efficacy Estimand

The analysis related to efficacy estimand will be conducted utilizing data in the EAS.

For the mean percent body weight change from randomization, a MMRM will be conducted. Restricted maximum likelihood (REML) will be used to obtain model parameter estimates and the Kenward-Roger option will be used to estimate the denominator degrees of freedom. The response variable of MMRM will be the percent change in body weight from baseline values obtained at each scheduled post baseline visit.

For the percentage of participants achieving at least 5% body weight reduction from randomization over time, a logistic regression model will be used with the response variable of the percentage of participants achieving at least 5% body weight reduction at each scheduled postbaseline visit.

For MMRM the independent variables of analysis model is treatment group, visit, treatment-by-visit interaction, stratification factors (prediabetes status at randomization, sex and country/pooled country) as fixed effects, and baseline body weight as a covariate. An unstructured covariance structure will model relationship of within-patient errors. If this model fails to converge, the following variance covariance structures will be tested in order until convergence is achieved:

- heterogeneous Toeplitz
- heterogeneous first order autoregressive
- heterogeneous compound symmetry
- Toeplitz
- first order autoregressive, and
- compound symmetry.

The first covariance structure that converges will be used.

With the aid of the MMRM analysis, 2-sided 95% CIs for mean percent change in body weight from randomization to the 72-week visit for tirzepatide 10 mg and 15 mg compared to placebo will be derived and summarized. The resulting least squares mean (LSM) estimates of mean percent change in body weight from baseline will be plotted by visit and by study treatment.

A logistic regression model with terms of treatment group, country/pooled country, sex, and prediabetes status at randomization as fixed effects, and baseline body weight as a covariate, will be conducted for percentage of participants achieving at least 5% body weight reduction from randomization at the 72 week visit. Missing body weight measurement at 72 week will be imputed by the predicted value from MMRM model aforementioned, then the continuous measurements will be dichotomized into status of achieving at least 5% body weight reduction

(Yes or No). A logistic regression will be utilized to analyze proportion of participants with at least 5% body weight reduction at each nominal visit from randomization through 72 weeks.

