- review of participant diary information (to include reinforcement and compliance assessments for study drug administration and lifestyle goals)
- administration of questionnaires
- laboratory testing
- drug dispensing
- collect AEs, product complaints and concomitant medications

Mental Health Questionnaires should be completed after the assessment of AEs.

Dietician consultations continue at Weeks 4, 8, 12, and then every 12 weeks thereafter, to Week 72. Study drug and injection supplies will be returned per the Schedule of Activities (Section 1.3) and according to local requirements. New supplies will be dispensed as needed.

Study drug dose escalation is double-blinded and will be managed via the interactive web-response system (IWRS). The starting dose is 2.5 mg QW (or matching placebo) for 4 weeks, then the dose is increased by 2.5 mg (or matching placebo) every 4 weeks: 2.5 to 5 mg for those randomized to 5 mg, 2.5 to 5 to 7.5 to 10 mg for those randomized to 10 mg, and continuing to 12.5 to 15 mg for those randomized to 15 mg. The dose is then maintained up to 72 weeks.

At each of the 8 scheduled telephone visits, procedures will include:

- reinforcement and compliance assessments for study drug administration and lifestyle goals,
- listing of concomitant medications
- AE and Product Complaints (PCs) assessment (see Schedule of Activities Section 1.3.1)
- administration of questionnaires

Participants should be instructed to contact the investigative site for assistance as soon as possible if they experience any difficulties administering their study medication. Participants should also be advised about the appropriate course of action in the event that study drug is not taken at the required time (late/missing doses).

Study participants will be permitted to use concomitant medications that they require during the study, except certain excluded medications (see Section 5.2) that may interfere with the assessment of efficacy and safety characteristics of the study treatments.

For those participants without glycemic evidence of T2DM (Section 4.1.2.1), a 2-hour oral OGTT will be performed at Visit 21.

Visit 99

Visit 99 is only applicable to participants who discontinue the study treatment prematurely (before Week 72). Participants will be asked to return for Visit 99 at 72 weeks \pm 7 days after

randomization. This visit is critical to ensure complete data collection for the primary weight-loss endpoint.

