9.2. Sample Size Determination

Approximately 3429 participants will be screened to achieve 2400 randomly assigned to study intervention (600 participants per intervention group).

The sample size determination assumes that evaluation of superiority of 10-mg tirzepatide and tirzepatide 15 mg to placebo will be conducted in parallel, each at a 2-sided significance level of 0.025 using a 2-sample t-test. Additionally, a difference of at least 11% mean body weight percentage reduction from randomization at 72 weeks for 10-mg tirzepatide and/or tirzepatide 15 mg compared with placebo, a common SD of 10%, and a dropout rate of 25% are assumed for statistical power calculations. Under the assumptions above, randomizing 2400 participants in a 1:1:1:1 ratio to tirzepatide 5 mg (600), tirzepatide 10 mg (600), tirzepatide 15 mg (600), and placebo (600) provides more than 90% power to demonstrate superiority of tirzepatide 10 mg and/or 15 mg to placebo.

The chosen sample size and randomization ratio also provides >90% power to establish superiority of 10-mg tirzepatide and 15-mg tirzepatide doses to placebo in term of percentage of participants achieving at least 5% body weight reduction at 72 weeks, conducted in parallel using a Fisher's exact test, each at a 2-sided significance level of 0.025, assuming 25% placebo-treated participants and 90% tirzepatide-treated participants achieving the goal and a dropout rate of 25%.

In addition, assuming that approximately 60% of the randomized population will have prediabetes, the study sample size will also provide more than 90% power to demonstrate superiority of tirzepatide (all doses combined) over placebo in terms of delaying the onset of diabetes for participants with prediabetes at study entry. It is based on the following assumptions: 1.6% (corresponding to annual hazard rate of 0.54%) of participants randomized to tirzepatide and 6% of participants randomized to placebo (corresponding to annual hazard rate of

2.1%) will progress to diabetes during the 3-year period; 49% of participants will drop out (corresponding to annual drop-out rate of 22%) during the same period; and the test will be conducted at a 2-sided significance level of 0.05.

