9.4. Statistical Analyses

9.4.1. General Statistical Considerations

Statistical analysis of this study will be the responsibility of Lilly or its designee. Any change to the data analysis methods described in the protocol will require an amendment ONLY if it changes a principal feature of the protocol. Any other change to the data analysis methods described in the protocol, and the justification for making the change, will be described in the SAP or the Clinical Study Report (CSR). Additional exploratory data analyses may be conducted as deemed appropriate.

Unless otherwise noted, all tests of treatment effects will be conducted at a 2-sided alpha level of 0.05, and the confidence interval will be calculated at 95%, 2-sided. In statistical summaries and analyses, data will be analyzed as randomized.

Unless specified otherwise, efficacy and safety will be assessed using the modified intention-to-treat (mITT) population. Baseline will be defined as the last available non-missing measurement during Visit 1 to Visit 3. Unless specified otherwise, safety assessments will be guided by an estimand comparing safety of tirzepatide doses with placebo irrespective of adherence to study drug. Thus, safety analysis will be conducted using safety analysis set (SS).

Summary statistics for continuous measures will include sample size, mean, SD, median, minimum, and maximum. The analysis model to make comparisons among treatment groups relative to continuous measurements assessed over time will include a mixed model for repeated measures (MMRM), with terms of treatment, visit, and treatment-by-visit interaction, stratification factors, and baseline measurement as a covariate.

Kaplan-Meier method will be used for estimation of cumulative event-free survival rates over time, and Cox proportional hazards regression analysis will be used to compare hazard rates among treatments.

Summary statistics for categorical measures (including categorized continuous measures) will include sample size, frequency, and percentages. Logistic regression will be used to examine the treatment difference in binary efficacy outcomes if there is a need to adjust for covariates.

Otherwise, Fisher's exact test will be used to examine the treatment difference in categorical outcomes.

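### Efficacy-estimand MMRM: covariate effects are fixed across visits, so adjustment at Week 72 can be largely lost if those effects grow with time

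*SAP*

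**What the plan says.** SAP 6.13.1.1 specifies the MMRM for the efficacy estimand. On the outcome it says: "The response variable of MMRM will be the percent change in body weight from baseline values obtained at each scheduled post baseline visit". The fixed effects are "treatment group, visit, treatment-by-visit interaction, stratification factors (prediabetes status at randomization, sex and country/pooled country) as fixed effects", and the specification continues "and baseline body weight as a covariate. An unstructured covariance structure will model relationship of within-patient errors". Protocol 9.4.1 has the same form: an MMRM "with terms of treatment, visit, and treatment-by-visit interaction, stratification factors, and baseline measurement as a covariate". Neither document crosses any covariate with visit.

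SAP 6.13 makes this the main analysis for every purpose other than the FDA submission. For the FDA, SAP 6.13.1.2 uses an ANCOVA of the Week-72 value alone, with the same covariates.

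The full subgroup model in SAP 6.16.1 does cross each subgroup factor with visit, and sex and glycemic status are among those factors.

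**The concern.** A covariate with a single coefficient is assumed to shift percent weight change by the same amount at Week 4 and at Week 72. That is unlikely for a change-from-baseline outcome. Everyone starts at zero, and on active drug the dose starts low, "then the dose is increased by 2.5 mg (or matching placebo) every 4 weeks". A factor that matters for weight loss may therefore show little effect early and more later.

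Generalized least squares estimates the shared coefficient by weighting visits by their precision. If early values vary little, they dominate the estimate. The model could then subtract almost nothing at Week 72, and covariate variation would stay in the residual. What is at stake is precision at the primary time point in the analysis used outside the FDA submission.

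**Working it through.** **1. The plan's own power figure.** Protocol 9.2 tests each dose "each at a 2-sided significance level of 0.025 using a 2-sample t-test", with "a difference of at least 11% mean body weight percentage reduction from randomization at 72 weeks" and "a common SD of 10%, and a dropout rate of 25% are assumed for statistical power calculations". Evaluable per arm: 600 × 0.75 = 450. Standard error: 10 × √(2/450) = 0.667. Noncentrality: 11 / 0.667 = 16.5. Power is above 99.9%, so the stated figure of more than 90% reproduces. The SD of 10% is for Week 72; no SD is given for any earlier visit.

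**2. What the shared slope estimates.** The schedule in Protocol 1.3.1 has ten post-baseline weights to Week 72 (Weeks 4, 8, 12, 16, 20, 24, 36, 48, 60, 72). Let b be the vector of true covariate effects at these visits, b72 its Week-72 element, and S the within-patient covariance. With complete data:

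- shared slope: β = (1′S⁻¹b) / (1′S⁻¹1)
- share of the Week-72 variance reduction that is kept: 1 − (1 − β/b72)²

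**3. Share kept.** The effect and the SD both rise from Week 4 to Week 72 along a saturating curve. Ranges are over autoregressive correlation (0.85 to 0.95 per 4 weeks, with and without measurement noise) and exchangeable correlation (0.5 and 0.8). All of these are assumptions.

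| SD at Week 4 (10% at Week 72) | Week-4 effect 10% of Week-72 effect | 20% | 50% | 100% |
|---|---|---|---|---|
| 2% | −19% to 11% | 6% to 30% | 63% to 73% | 100% |
| 4% | −68% to 40% | −33% to 53% | 48% to 82% | 100% |
| 10% (constant) | 84% to 88% | 87% to 90% | 95% to 96% | 100% |

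A negative entry means slightly worse than no adjustment. Large loss requires both a growing spread and an effect that is small at Week 4.

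**4. Cost in precision.** Simulated complete data: 2,400 participants, ten visits, SD rising from 2% to 9.5%, Week-72 sex effect 3 to 5 points, baseline-weight effect 0 to 1.5 points per SD. The variance of the Week-72 contrast, shared slope over by-visit slopes, was 1.022, 1.040, 1.051 and 1.088 in four scenarios. Square roots: 1.011, 1.020, 1.025, 1.043, so the standard error is 1.1% to 4.3% larger.

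At the planning inputs the 95% half-width is 1.96 × 0.667 = 1.31 points. The excess is 1.31 × 0.011 = 0.01 to 1.31 × 0.043 = 0.06 points, against a planned difference of 11.

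**5. Upper limit.** Losing the whole adjustment multiplies the variance by 1/(1 − R²), where R² is the share of Week-72 variance that the covariates explain: 1.02, 1.05, 1.11 and 1.25 for R² of 2%, 5%, 10% and 20%. The largest ratio in step 4 corresponds to R² of about 1 − 1/1.088 = 8%. A separate simulation with 600 per arm and SD rising from 2% to 10% gave standard errors, shared slope against by-visit slope, of 0.576 against 0.563 at R² = 5% (ratio 1.02) and 0.572 against 0.516 at R² = 20% (ratio 1.11). The shared slope was 0.02 of the true Week-72 slope; with the interaction it was 0.97 to 0.98.

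**The case against.** The strongest reply is that the premise is inferred. The documents give one SD, at Week 72, and no covariate effect at any visit. Diet counselling starts at Visit 3, so effects could already be present at Week 4. If the Week-4 effect is half the Week-72 effect, roughly half to four fifths of the adjustment is kept when the SD rises from 2–4% to 10%. If effects are constant, all of it is kept. This stands, and it is why the conclusion is conditional. An unconditional claim that the adjustment is largely lost is not supported.

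It is also fair to say that no decision changes. Power exceeds 99.9% either way, and with complete data the simulated estimates showed no bias attributable to the model. The model is prespecified and valid.

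Three further inferences are tempting and not supported:

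- **Weaker responder analyses.** The logistic model in SAP 6.13.1.1 has its own covariates at Week 72. The MMRM only fills in missing weights, and no effect on responder results was calculated.
- **A stated loss for waist circumference or Week 176.** These models refer back to this one, but no size was computed for them.
- **A conflict between the two estimands.** They use different data and models by design; the difference in adjustment is not a contradiction.

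Crossing country with visit as well would add many parameters and call for a second convergence fallback beside the SAP's ordered list of covariance structures. That objection is accepted in the fix.

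**Conclusion.** The point holds as a low-cost improvement. The model has one effect per covariate for all visits, and under a growing spread the estimate of that effect leans on early visits. Adjustment at Week 72 can then be largely lost if covariate effects start small and grow. Under the inputs in step 4 the standard error is about 1% to 4% larger than necessary; it would be more only if the covariates explain more than about 8% of Week-72 variance. All early-visit SDs, correlations and covariate effects are assumptions.

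Power and complete-data validity are not in question, and the hybrid-estimand ANCOVA is untouched. A reader might also infer bias under dropout. With 25% dropout made to depend on both covariate and arm, simulated estimates were −11.27 and −11.28 with the shared slope, against −11.07 and −11.12 with by-visit slopes (truth −11). That pattern is assumed, since the documents give only an overall rate. There were 40 replicates with empirical SDs of 0.55 to 0.61, so each mean carries a Monte Carlo error of about 0.6/√40 = 0.09. This does not establish a bias in this trial.

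**What to change.** In SAP 6.13.1.1, add baseline-weight-by-visit, sex-by-visit and prediabetes-by-visit interactions to the MMRM, and keep country/pooled country as a main effect. In the models that refer to this section, use the corresponding baseline-by-visit and sex-by-visit terms. Align the general description in Protocol 9.4.1, or state in the SAP that it is refined there.

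Cost to Week 72: three one-parameter covariates × 9 additional visits = 27 more fixed effects, with about 2,400 participants. The Week-176 weight model, in participants with prediabetes only, has 18 post-baseline weights, so baseline and sex add 2 × 17 = 34. The fit is slightly heavier. If effects are in fact constant, almost no precision is lost; if they grow, the Week-72 adjustment is restored.

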6.14. Safety Analyses

Unless specified otherwise, safety assessments will be based on the SS (Table GPHK.6.1). All events that occur between the first dose date of study drug and the end date of study participation will be included, regardless of the adherence to study drug.

The statistical assessment of homogeneity of the distribution of categorical safety responses between tirzepatide doses and placebo will be conducted using Fisher's exact test, unless specified otherwise.

For selected continuous safety parameters, the mean change from baseline differences vs. placebo will be assessed via a MMRM using REML. Data from scheduled visits will be utilized for this analysis. Unless specified otherwise, the model for the analysis during 72 weeks treatment period will include country/pooled country, sex, prediabetes status at randomization, treatment group, visit and treatment-by-visit interaction as fixed effects, and baseline value of the safety parameter as a covariate. For the analysis during the 176 weeks treatment period (or 193 weeks), only participants with prediabetes at randomization in the SS will be included, and the model will contain the terms of country/pooled country, sex, treatment group, visit and treatment-by-visit interaction as fixed effects, and baseline value of the safety parameter as a covariate. To model the covariance structure within participants, the unstructured covariance matrix will be used. If this model fails to converge, the covariance structures specified in Section 6.13.1.1 will be tested in order until met convergence. If the data does not warrant the MMRM model, then ANCOVA model will be conducted.

For selected safety parameters, time-to-first-event analysis via the Cox-proportional hazards model may be conducted. Participants without the event will be censored at the end of study participation. For participants experiencing the event, the "time-to-first-event" will be the time (in days) from first dose to first occurrence of the event.

Where necessary, the rate of events will be analyzed using a generalized linear mixed-effects model assuming the number of events follow a negative binomial distribution and with treatment as a fixed effect. The logarithm of days during the active treatment period will be adjusted as an offset to account for possible unequal treatment duration of follow-up between participants.

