6.16.1. Subgroup Analysis of Body Weight Change

Subgroup analyses by the following baseline characteristics will be provided:

- age group (<65, ≥65 years)
- race
- sex
- ethnicity
- region of enrollment (US, outside of US [OUS])
- body mass index group (<30, ≥30 and <35, ≥35 and <40, ≥40 kg/m²), and
- glycemic status at randomization (normoglycemia vs prediabetes).

The outcome measures for the subgroup analyses will include:

- percent change in body weight from randomization at 72 weeks and
- percentage of participants achieving at least 5% body weight reduction at 72 weeks.

For the percentage change in body weight from randomization at 72 weeks, for each subgroup analyses aforementioned, the following 2 models will be conducted:

- Conduct MMRM model on the subgroup only with terms of treatment group, visit, treatment-by-visit-interaction, country/pooled country, sex, and prediabetes status at randomization as fixed effects, and baseline body weight as a covariate. Variance-covariance structure for within-patient errors will be same as Section 6.13.1.1
- Full MMRM model: treatment group, visit, subgroup, treatment-by-visit-interaction, treatment-by-subgroup-interaction, subgroup-by-visit-interaction, treatment-visit-subgroup-interaction, country/pooled country, sex, and prediabetes status at randomization as fixed effects, and baseline body weight as a covariate. Variance-covariance structure for within-patient errors will be same as Section 6.13.1.1.

For the percentage of participants achieving at least 5% body weight reduction at 72 weeks, for each subgroup analyses aforementioned, the following 2 models will be conducted:

- Conduct logistic regression model on the subgroup with terms of treatment group, country/pooled country, sex and prediabetes status at randomization as fixed effects, and baseline body weight as covariate. Missing body weight measurement at 72 weeks will be imputed by the predicted value from MMRM model on the subgroup aforementioned, then the continuous measurements will be dichotomized into status of achieving at least 5% body weight reduction (Yes or No).

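### If the unstructured MMRM fails, the first fallback that converges is used with model-based standard errors, so Week-72 intervals can be mis-sized; an empirical standard error should be specified

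*SAP*

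**What the plan says.** SAP 6.13.1.1 (efficacy estimand) fits percent change in weight by REML: "An unstructured covariance structure will model relationship of within-patient errors". On degrees of freedom, "the Kenward-Roger option will be used to estimate the denominator degrees of freedom". The fallback is triggered by non-convergence alone: "If this model fails to converge, the following variance covariance structures will be tested in order until convergence is achieved". The order is heterogeneous Toeplitz, heterogeneous AR(1), heterogeneous compound symmetry, Toeplitz, AR(1), compound symmetry, and "The first covariance structure that converges will be used". The output is "2-sided 95% CIs for mean percent change in body weight from randomization to the 72-week visit", for 10 mg and 15 mg against placebo.

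The rule reaches further by reference. SAP Table GPHK.6.4 reuses this MMRM for key secondary endpoints. SAP 6.14 says that for safety parameters "the covariance structures specified in Section 6.13.1.1 will be tested in order until met convergence". SAP 6.16.1 says for the subgroup models "Variance-covariance structure for within-patient errors will be same as Section 6.13.1.1".

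The SAP names no fit criterion, no empirical (sandwich) estimator, no step to rescue the unstructured fit and no sensitivity analysis for a fallback. That standard errors are model-based is an inference from the Kenward-Roger option and this silence. It is the natural reading.

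**The concern.** A model-based standard error is right only if the fitted covariance is right. Convergence is a numerical event and does not test that. Two features of the trial make misfit likely for body weight.

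- Unequal spacing. Weight is measured every 4 weeks to Week 24 and every 12 weeks after that. Toeplitz and AR(1) index correlation by visit order, so they treat a 4-week gap and a 12-week gap alike.
- Growing spread. Percent change is zero at baseline by definition, so its variance can be expected to rise towards Week 72. The last three structures on the list force one variance on all visits.

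At stake are the width of the reported intervals and the nominal error rate of the MMRM p-values in the efficacy-estimand, safety and subgroup analyses, if a fallback is used.

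**Working it through.** **The plan's own figure.** Protocol 9.2 assumes 600 per arm, 25% dropout, SD 10, a difference of 11 points, and tests "each at a 2-sided significance level of 0.025 using a 2-sample t-test".
- n per arm = 600 × 0.75 = 450
- SE = 10 × √(2/450) = 0.667
- z = 11 / 0.667 = 16.5
- Power exceeds 99.9%, consistent with the stated figure of more than 90%.

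**Size of the models.** A model with p visits has p(p+1)/2 unstructured covariance parameters.
- 72-week weight model: Weeks 4, 8, 12, 16, 20, 24, 36, 48, 60, 72, so p = 10 and 10 × 11 / 2 = 55 parameters, for about 2400 participants.
- 176-week model: eight more office visits (Weeks 85 to 176), so p = 18 and 18 × 19 / 2 = 171 parameters, for participants with prediabetes only.

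**From a standard-error ratio to error rates.** Let r = model SE / true SE at Week 72.
- 95% CI coverage = 2Φ(1.96 r) − 1
- Type I error at 2-sided 0.025 = 2[1 − Φ(2.241 r)]

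**A case that can be checked by hand.** Suppose the SD grows as the square root of time to 10 at Week 72, and there is no dropout. Compound symmetry then estimates the average of the visit variances.
- Mean visit week = 300 / 10 = 30, so the pooled variance = 100 × 30/72 = 41.7 and the pooled SD = 6.45.
- Week 72: r = 6.45 / 10 = 0.645. Coverage is 79% and type I error 0.148.
- Week 20: true SD = √(100 × 20/72) = 5.27, so r = 6.45 / 5.27 = 1.22. The error goes the other way.

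**With dropout, over a range of assumed covariances.** The documents give no visit-specific SDs or correlations, so these are assumptions. There are 18 true covariances: the SD rises from 1.5, 2, 2.4 or 7 to 10, crossed with four correlation patterns, plus Brownian, plus random intercept and slope with error. Each uses 10 visits, 600 per arm and 25% dropout completely at random. For each fallback, the limiting likelihood fit gives the model SE, which is compared with the true SE. Coverage and error below follow from the rounded ratios.

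| Fallback | r at Week 72 | 95% CI coverage | Type I error (nominal 0.025) |
|---|---|---|---|
| Heterogeneous Toeplitz | 0.76 to 1.22 | 86% to 98% | 0.09 to 0.006 |
| Heterogeneous AR(1) | 0.76 to 1.20 | 86% to 98% | 0.09 to 0.007 |
| Heterogeneous CS | 0.94 to 1.06 | 93% to 96% | 0.035 to 0.018 |
| Toeplitz | 0.57 to 0.85 | 74% to 90% | 0.20 to 0.057 |
| AR(1) | 0.56 to 0.86 | 73% to 91% | 0.21 to 0.054 |
| CS | 0.49 to 0.84 | 66% to 90% | 0.27 to 0.060 |

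For heterogeneous Toeplitz and AR(1) the sign depends on the true correlation:
- decay with calendar time, exp(−Δt/100): 1.22 and 1.20 (too wide)
- compound symmetric: 1.00 and 1.02 (about right)
- Brownian or log-time: 0.90 to 0.91 (too narrow)
- random intercept and slope: 0.76 and 0.76 (too narrow)

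At 10% dropout the ranges are similar: 0.76 to 1.23 for the heterogeneous structures and 0.52 to 0.86 for the homogeneous ones. At Week 20 the homogeneous structures give r of about 1.01 to 2.1.

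**Does a sandwich SE repair it?** A separate simulation ran 2,500 null trials with 600 per arm, about 26% MAR dropout, SD rising from 5 to 10 and correlation 0.93 per 8 weeks. Rejection at 0.025, model-based then sandwich:
- heterogeneous Toeplitz 0.008, 0.026; heterogeneous AR(1) 0.007, 0.020; heterogeneous CS 0.020, 0.028
- Toeplitz 0.114, 0.021; AR(1) 0.109, 0.030; CS 0.151, 0.028

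With a flat SD of 10, model-based rejection under the homogeneous structures was 0.023 to 0.044, so most of their inflation comes from growing spread. In the 18-covariance check, the true SE under a fallback was 1.00 to 1.07 times the unstructured SE, so little precision is lost.

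**The case against.** The rule is fully prespecified (default, trigger, order and stopping point), so it leaves no data-driven choice. The unstructured 72-week model is unlikely to fail, and the largest errors need four successive failures: unstructured and then all three heterogeneous structures. Both points stand, and no probability of failure can be drawn from the documents.

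The reach is also narrower than the cross-references suggest:
- The FDA primary analysis (hybrid estimand, SAP 6.13.1.2) is ANCOVA with multiple imputation and involves no covariance structure.
- Lipids have only two scheduled on-treatment visits, Weeks 24 and 72. The unstructured matrix then has 3 parameters and is the same as heterogeneous Toeplitz.
- Fasting insulin and HbA1c are drawn at equally spaced visits (Weeks 12 to 72), so the spacing argument does not apply to them up to Week 72.
- Growing spread is an argument about weight change. Nothing in the documents shows it for blood pressure, lipids or safety measures.
- SAP 6.14 allows ANCOVA if the data do not support the MMRM. Safety and subgroup analyses carry no multiplicity-controlled level, so coverage is the relevant measure there, not the 0.025 error rate.

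A reader might infer that the first fallbacks always give intervals that are too wide and the last three always give intervals that are too narrow. The documents do not support this. The heterogeneous structures keep their own Week-72 variance parameter, and their error depends on correlations that the documents do not give. The homogeneous ones are too narrow at Week 72 only if spread grows, and they tend to be too wide at Week 20.

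What survives is that, once triggered, the rule can yield wrong standard errors of unknown direction, and nothing in the SAP would detect or correct this.

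**Conclusion.** The concern holds as a conditional weakness. If a fallback is used, Week-72 standard errors for weight can be off by roughly a quarter in either direction under heterogeneous Toeplitz or AR(1). They are close to right under heterogeneous compound symmetry. Under the three homogeneous structures they are about 14% to 50% too small if spread grows.

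The trigger is most plausible in the 176-week model (171 covariance parameters) and the small subgroup-only models. The primary weight conclusion is not at risk: at the planned effect, dividing z = 16.5 by ratios from 1.22 to 0.49 gives 13.5 to 33.7, far above 2.241. Interval width and nominal error are what change.

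These sizes rest on assumed covariances and dropout patterns. They ignore covariate terms and the Kenward-Roger adjustment, which is small at 600 per arm. The label is cheap improvement.

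**What to change.** In SAP 6.13.1.1, carried by reference into 6.14 and 6.16.1, state two things.

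1. If the unstructured model does not converge, it is first refitted with supplied starting values and Fisher scoring.
2. If a fallback structure is still needed, standard errors, confidence intervals and p-values use the empirical (sandwich) covariance estimator, with a named small-sample correction and between-within degrees of freedom, in place of Kenward-Roger.

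Keep the fallback list as it stands. Deleting the homogeneous structures might look natural, but it would leave no specified analysis if heterogeneous compound symmetry also failed, and the sandwich error brings all six close to nominal.

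The cost is two sentences, one procedure option in the MMRM programs and no new data. It should be settled before unblinding, so that the choice of standard error is not made after a convergence failure is seen.

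There are two limits. Sandwich errors are somewhat less stable in small subgroups, which is why the correction should be named. They also correct the variance only, not any bias in the Week-72 estimate from a misspecified covariance under MAR dropout. Nor do they correct the MMRM predictions that fill in missing weights for the 5% responder analysis. The first step, rescuing the unstructured fit, is the part that helps there.
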